We will also quantify the percentage of observant and non observant patients, as well as the percentage of responsive and non-responsive patients. While observance will be based on the use of the sensor, responsiveness will be based on "safe" UV behaviors. Observance will be defined as at least 50% of days used, poor observance between 15% to 50% and non-observance as inferior to 15%. Responsiveness will be defined as less than 15% days over the UV threshold and more than 85% of days with an UV threshold set within one standard deviation of the study group's average UV threshold. Conversely, non-responsiveness is defined as more than 15% days over the UV threshold or more than 85% of days with an UV threshold set above one standard deviation of the study group's average UV threshold.

The sociodemographic and clinical characteristics of observant, poorly observant, non-observant, responsive and non-responsive patients will be assessed separately and compared using Student's t-tests for quantitative characteristics and  $\chi^2$  for categorical characteristics. These comparisons will provide useful information to better understand the determinants of UV behaviour change.

To be conservative, only non-observant subjects (<15% of days use) will be excluded from the analyses while poorly and non-responsive patients will be included. The comparison of their characteristics will rule out a selection bias.

**#10 (Secondary): Assess feasibility of the intervention for kidney transplant recipients through report of their rates for compliance and retention.**

Rates will be reported but are not expected to be analyzed for significance.

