## 10.4.10 TABULATION OF INDIVIDUAL RESPONSE DATA

Clinical data tables will be reduced into a table of individual responses for analysis as follows:

Column	Source (name of CRF with data)
SubjectID	N/A
AK baseline (count)	Actinic Keratosis
AK follow up (cumulative count)	Actinic Keratosis
NMSC baseline (count)	NMSC
NMSC follow up (cumulative count)	NMSC
Observant % of days	Compliance database
Responsive Y/N	Shade database: days with UV limit below 90% of exposures
CPD R 0	Lab data
CPD R 12 month	Lab data
MHA 1	PROMIS MHA visit 1
MHA 2	PROMIS MHA visit 2
MHA 3	PROMIS MHA visit 3
MHD 1	PROMIS MHD
MHD 2	PROMIS MHD
MHD 3	PROMIS MHD
SHP 1	PROMIS SHP
SHP 2	PROMIS SHP
SHP 3	PROMIS SHP
UV Ave	Sensor data
AE (count)	CRF
comment	

group	Randomization
exclude	

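### In endpoint #9 the responsive and non-responsive rules leave some device users in neither class, and the analysis table codes responsiveness by a different rule

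*Combined protocol and SAP*

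**What the plan says.** Section 10.4.3, endpoint #9, states the purpose of the classification: "responsiveness will be based on 'safe' UV behaviors". It then gives two rules.

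- Responsive, two conditions joined by *and*: "Responsiveness will be defined as less than 15% days over the UV threshold", together with "more than 85% of days with an UV threshold set within one standard deviation of the study group's average UV threshold".
- Non-responsive, two conditions joined by *or*. One is exceeding the limit on over 15% of days. The other is "more than 85% of days with an UV threshold set above one standard deviation of the study group's average UV threshold".

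The percentage in each class is to be reported, and the sociodemographic and clinical characteristics of the classes are to be compared with t-tests and chi-squared tests. The same section says that users choose their own threshold, that the app recommends none, and that every subject is counseled to minimize UV exposure.

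Section 10.4.10 lists a single yes/no variable for responsiveness. Its source is given as "Shade database: days with UV limit below 90% of exposures".

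**The concern.** The second rule is introduced as the converse of the first but is not its complement. The first uses a band on both sides of the group average; the second uses only the upper edge of that band. A user can therefore fail the first rule without meeting the second. One such user sets a low threshold and keeps under it, which is a foreseeable response to the counseling.

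At stake is endpoint #9 itself. The two percentages need not add to 100%. The comparison of characteristics, meant to explain what drives change in UV behaviour, can omit patients for a reason tied to that behaviour. The yes/no variable in section 10.4.10 has no place for a user in neither class, and its rule is a different one. Two analysts could therefore classify the same data differently.

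**Working it through.** The plan states no figure for the size of either class, so there is nothing to reproduce. The check is one of logic, followed by a range for the possible size of one gap.

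**Notation** (percent of a user's days)

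- a = days over the threshold
- h = days with the threshold above mean + 1 SD
- l = days with the threshold below mean − 1 SD
- w = 100 − h − l = days with the threshold inside the band

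**Rules from section 10.4.3, #9**

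- Responsive: a < 15 and w > 85
- Non-responsive: a > 15 or h > 85
- True complement of responsive: a ≥ 15 or w ≤ 85

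**Overlap.** Responsive needs a < 15, and w > 85 forces h < 15. Neither non-responsive condition can then hold, so no user is in both classes.

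**Gap.** A user is in neither class if a < 15, h + l ≥ 15 and h ≤ 85, or if a = 15 and h ≤ 85. Examples:

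| a | w | h | l | Class as written |
|---|---|---|---|---|
| 5 | 100 | 0 | 0 | responsive |
| 0 | 0 | 0 | 100 | neither |
| 5 | 80 | 0 | 20 | neither |
| 5 | 50 | 50 | 0 | neither |
| 15 | 100 | 0 | 0 | neither |
| 40 | 0 | 0 | 100 | non-responsive |

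**Enumeration over whole percentages.** There are 101 values of a and 5,151 pairs (h, l), so 520,251 combinations. Of the pairs, 120 have w > 85 and another 120 have h > 85.

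- Responsive: 15 × 120 = 1,800
- Neither: 15 × (5,151 − 240) + (5,151 − 120) = 73,665 + 5,031 = 78,696
- Non-responsive: 520,251 − 1,800 − 78,696 = 439,755

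These are counts of logical cases, not of patients. They show that the gap is not confined to one boundary value.

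**One-sided reading.** Suppose the band is taken to mean only that the threshold is not above mean + 1 SD. Responsive then needs a < 15 and h < 15, and 1,410 pairs have h < 15. The number in neither class is 15 × (5,151 − 1,410 − 120) + 5,031 = 54,315 + 5,031 = 59,346. The low-side gap closes. Users with 15 ≤ h ≤ 85 and a ≤ 15, and users at a = 15 with h ≤ 85, remain in neither class.

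**Possible size of the low-side gap.** Section 4.1 plans 120 patients, half with the sensor: 60. The documents give no mean, SD or shape for the threshold, so these are assumptions, with the SD taken across patients.

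- Normal: Φ(−1) = 0.159; 0.159 × 60 = 9.5.
- Lognormal with coefficient of variation CV: share = Φ((ln(1 − CV) + s²/2)/s), where s² = ln(1 + CV²). For CV 0.5, s² = ln 1.25 = 0.223 and s = 0.472, so the share is Φ((−0.693 + 0.112)/0.472) = Φ(−1.23) = 0.109, or 6.5 of 60.
- Other lognormal cases: CV 0.2, 15.2% (9.1 of 60); CV 0.3, 14.3% (8.6); CV 0.75, 4.1% (2.4); CV 0.9, 0.5% (0.3); CV 1 or more, 0, because mean − 1 SD is then not positive.

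Each count is an upper bound for its distribution, because it supposes that every low-threshold user is over the limit on no more than 15% of days. Users in the mixed-day and exactly-15% gaps come on top and cannot be sized from the documents.

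**Section 10.4.10 beside section 10.4.3.** The table entry uses 90%, has no SD band and no 15% or 85% cut, and does not say how a number of days becomes yes or no. Without a band it cannot reproduce the threshold condition of endpoint #9.

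**The case against.** The best case for leaving the text alone has five parts.

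- *The band may have been meant one-sided.* That would close the low-side gap. The other two gaps and the mismatch with section 10.4.10 would remain, so the point survives either reading.
- *Few patients may be affected.* This stands. A reader might infer from the normal tail that 9 or 10 of 60 device users will be unclassified. The documents do not support that. It assumes a normal distribution for a user-chosen, non-negative quantity and assumes that all these users keep under their limit. A lower limit is easier to exceed, and anyone over it on more than 15% of days is already non-responsive.
- *Being under a low limit need not mean the safest behaviour.* This also stands. Logging sunscreen lowers the reported dose for 90 minutes, a covered sensor does not register UV, and users with as little as 15% of days used are kept. The gap takes in users with a low limit and few recorded exceedances. Calling them the most protective users would go further than the documents allow.
- *The table entry is only a terse data-source note.* That is fair as to tone, but it is the only specification of the analysis variable, and it disagrees with the text.
- *Nothing important depends on it.* Largely right. Endpoint #9 excludes only non-observant users (under 15% of days) from the analyses and keeps non-responsive ones.

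**Conclusion.** The point holds for secondary endpoint #9. As written, the two classes are mutually exclusive but not exhaustive, and section 10.4.10 codes responsiveness by a rule that does not match. The gaps apply only to users over their threshold on no more than 15% of days. The low-side gap also depends on the plain, two-sided reading of the band; the mixed-day and exactly-15% gaps do not.

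The low-side gap holds between 0 and about 9.5 of 60 device users under the assumed distributions, as an upper bound. The percentages may therefore fail to sum to 100%; whether they do depends on the data.

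A reader might also infer that the actinic keratosis result is at risk. It is not, because responsiveness decides nobody's inclusion in the primary analysis. This is a modest defect that should be corrected, because a stated rule misplaces patients for a listed endpoint. It should be settled before the blind is broken so that the definition is not chosen after seeing the data.

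**What to change.** In section 10.4.3, #9:

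1. Define responsive as less than 15% of days over the threshold **and** a threshold no higher than the group average plus 1 SD on more than 85% of days.
2. Define non-responsive as every other device user in the responsiveness analysis.
3. Use the same day denominator in both conditions, and say what it is.
4. State whether non-observant users (under 15% of days used) are classified at all, since they contribute little data.
5. Say whether the average and SD are taken across patients or across patient-days.

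In section 10.4.10, replace the source text for the responsive variable with this same rule.

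Applied to the six examples in the table above, the revised rule makes the first three responsive (including the low limit never exceeded) and the last three non-responsive. No case is left over. The cost is one paragraph of wording and one recoded variable; no new data are needed.

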#### 10.4.4 SAFETY ANALYSES

No safety analyses are planned.

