control group will not wear a sensor. This choice of control group allows us to provide standard of care advice to these subjects. The behavior change in the treatment group is expected to be a result of both the decision to engage with the device, for example by putting it on and opening the App as well as due to the knowledge of personal UV exposure reported by the device. We expect to gather information on the cumulative UV exposure of all subjects by using an ELISA assay for cyclopyridimine dimers (CPD) from photoexposed skin.

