## 2.3 POTENTIAL RISKS AND BENEFITS

### 2.3.1 KNOWN POTENTIAL RISKS

This is a minimal risk study. All subjects will, over the duration of the study, have one dermatology visit and skin check beyond the standard of care. Subjects in the treatment group will have additional information and interaction on their UV exposure to help them make the choice to minimize such exposure.

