## 3 OBJECTIVES AND PURPOSE

This study will evaluate the safety and effectiveness of Shade for the management of UV-induced skin complications and data collected from this study will be used to support the proposed indications for use.

The purpose of this investigation is to demonstrate the safety and effectiveness of the Shade UV sensor and mobile

phone application product to reduce actinic keratosis.

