# **8 ASSESSMENT OF SAFETY**

## **8.1 SPECIFICATION OF SAFETY PARAMETERS**

The primary safety endpoint is the number of adverse events related or possibly related to the device or sun exposure experienced within the study period. To test this hypothesis the number of adverse events related or possibly related to the device or sun exposure experienced by the treatment group should not be significantly greater than the number of adverse events related or possibly related to the device or sun exposure experienced by the control group throughout the duration of the study. Adverse events will be categorized by type, duration, severity, relationship to the study device and need for treatment.

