#### Relatedness

The potential event relationship to the study intervention and/or participation is assessed by the site investigator. A comprehensive scale in common use to categorize an event is:

- *Definitely Related*: The adverse event is clearly related to the investigational agent/procedure – i.e. an event that follows a reasonable temporal sequence from administration of the study intervention, follows a known or expected response pattern to the suspected intervention, that is confirmed by improvement on stopping and reappearance of the event on repeated exposure and that could not be reasonably explained by the known characteristics of the subject's clinical state.
- *Possibly Related*: An adverse event that follows a reasonable temporal sequence from administration of the study intervention follows a known or expected response pattern to the suspected intervention, but that could readily have been produced by a number of other factors.
- *Not Related*: The adverse event is clearly not related to the investigational agent/procedure. - i.e. another cause of the event is most plausible; and/or a clinically plausible temporal sequence is inconsistent with the onset of the event and the study intervention and/or a causal relationship is considered biologically implausible.

Mild sunburns, not requiring medical treatment, are expected to be over reported in the treatment group because of their constant communication with the application. These will not be considered AE's for the purposes of the safety endpoint.

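### Section 3 sets out to demonstrate safety and 8.1 gives a no-margin significance rule for it, but 10.4.4 plans no safety analysis, so a safety claim would be unsupported

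*Combined protocol and SAP*

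**What the plan says.** Four parts of the combined protocol and SAP bear on this.

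- **Section 3** sets the aim: "The purpose of this investigation is to demonstrate the safety and effectiveness of the Shade UV sensor" and its app. It adds that the data are meant to support the proposed indications for use.
- **Section 8.1** defines the endpoint: "The primary safety endpoint is the number of adverse events related or possibly related to the device or sun exposure" over the study period. It then gives a between-arm criterion, presented as the test of a hypothesis: the number of such events "experienced by the treatment group should not be significantly greater than the number of adverse events" of the same kind in controls. No margin, test, analysis population or expected rate is given. The section also requires that "Adverse events will be categorized by type, duration, severity, relationship to the study device and need for treatment".
- **Section 10.4.4** reads in full: "No safety analyses are planned".
- **Section 8.2.3**, under Relatedness, leaves mild untreated sunburns out of the safety endpoint, on the ground that "Mild sunburns, not requiring medical treatment, are expected to be over reported in the treatment group".

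On context, 2.3.1 says "This is a minimal risk study" and 2.2 says the "control group will not wear a sensor".

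**The concern.** A named primary endpoint with a significance criterion needs an analysis, and the analysis section says there is none. A statistician following 10.4.4 would produce nothing on safety. One following 8.1 would have to choose a test, population and unit of analysis that the plan does not give, and that choice affects the answer.

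The criterion is also of the wrong kind for the aim. Failing to show a significant increase is not the same as showing that there is no important increase, and with few events the two are far apart. Without a margin, sparse data make the rule easier to satisfy.

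The endpoint also pools two kinds of event. Both arms can have events caused by sun exposure, but controls can hardly have device-related events because they wear no sensor. A single pooled comparison can therefore dilute a device signal.

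At stake is whether the final report may say that safety was demonstrated, in support of the indications for use.

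**Working it through.** **1. Does any other section fill the gap?**
- 10.4.1 sets a two-tailed 0.05 level for all tests but names no test for adverse events.
- 10.4.7.1 rules out a specific safety review.
- 8.6 promises overall rates of hospitalization and AK, which are neither by arm nor the 8.1 endpoint.
- 10.4.10 lists an adverse event count per subject, with no stated use.
- The 0.81 power in 10.5 concerns AK counts only, so there is no safety figure to reproduce.

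The conflict therefore stands on the text alone. The rest of this working shows how little the 8.1 rule could establish.

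**2. Inputs for the illustration**
- From the documents: 120 patients, half to each arm (4.1), so 60 per arm; two-sided 0.05 (10.4.1).
- Assumed, because the documents give no rate: control rates of 0.02, 0.05, 0.10 and 0.20 events per patient, equal follow-up, and Poisson counts without clustering within patients.
- Expected control events, 60 × rate: 1.2, 3, 6 and 12. Under a true doubling the sensor arm expects 2.4, 6, 12 and 24.

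**3. Probability that a true doubling still passes**

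This is the probability that the result is not significant in the direction of harm. Two tests are shown because none is named. Student's t-test is what the plan uses for other lesion counts (10.4.2, and analysis #4 in 10.4.3); those figures come from simulation. The exact test treats the sensor-arm count, given the total, as binomial with probability 0.5 under equal rates.

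| Test | 0.02 | 0.05 | 0.10 | 0.20 |
|---|---|---|---|---|
| t-test, two-sided | 0.94 | 0.84 | 0.71 | 0.49 |
| exact, two-sided | 0.99 | 0.91 | 0.78 | 0.55 |
| t-test, one-sided | 0.84 | 0.73 | 0.59 | 0.36 |
| exact, one-sided | 0.97 | 0.85 | 0.67 | 0.41 |

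**4. Larger increases (exact test, two-sided)**
- Tripling: passes with probability 0.94, 0.69, 0.37 and 0.07.
- Ratio of 5: 0.72, 0.21, 0.02 and below 0.001.
- Ratio of 10: 0.15 at the lowest rate, and 0.001 or less at the others.

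**5. How many sensor-arm events pass against 0 control events?**

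*t-test, at most one event per patient.* With k events, the mean difference is k/60 and the sensor-arm variance is (k/60)(1 − k/60)(60/59). The control variance is zero, so SE = √(variance/60), on 118 df.
- k = 3: 0.0500/0.0284, t = 1.76, p = 0.081, passes.
- k = 4: 0.0667/0.0325, t = 2.05, p = 0.042, fails.

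*Exact two-sided test.* p = 2 × 0.5^k.
- k = 5: p = 0.0625, passes.
- k = 6: p = 0.031, fails.

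The largest passing count is 3 by one test and 5 by the other.

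**6. What an interval would show instead**

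With c events in each arm, let u be the 0.975 quantile of a Beta(c + 1, c) distribution. The exact 95% upper limit for the rate ratio is then u/(1 − u). For c = 3, 6 and 12 this gives 7.5, 3.7 and 2.4. Even identical counts would leave at least a doubling within the interval.

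**The case against.** The strongest reply is proportionality. The device is a clip-on sensor in a study described as minimal risk, and 8.6 records the sponsor's view that it is a non-significant risk device. Adverse events are still categorised (8.1), reported within 24 hours (8.4.1) and tabulated per subject alongside treatment group (10.4.10). A by-arm table could be made from the planned dataset, and the efficacy conclusion is unaffected. All of this stands. It makes descriptive safety reporting a reasonable choice, but Section 3 and 8.1 would then have to say so, and at present they say something else.

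A second reply is that the figures rest on assumed rates and on the choice of test. That also stands. At the lowest rate a doubling is 1.2 against 2.4 expected events, a small absolute excess. A reader might infer that the plan would accept marked imbalances such as 5 events against 0, 11 against 3, 16 against 6 or 24 against 12. The documents do not support that as a general statement. Those pairs pass a two-sided exact test (p = 0.063, 0.057, 0.052 and 0.065), but the plan never names that test. By a two-sided t-test with at most one event per patient they give p = 0.022, 0.023, 0.018 and 0.017, and all four fail. A one-sided exact test also fails all four (0.031, 0.029, 0.026 and 0.033), and the wording of 8.1 is directional.

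**Conclusion.** The point holds as a conflict between Section 3, 8.1 and 10.4.4, together with a criterion in 8.1 that cannot support the aim. The conflict needs no assumptions.

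The size of the weakness rests on assumed event rates, Poisson counts and 60 per arm. Under two-sided tests a true doubling would pass in roughly half of trials at 0.20 events per patient and in more than nine of ten at 0.02. One-sided tests lower these figures but do not change the conclusion.

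Two stronger readings should be resisted. The plan does not neglect adverse events, since they are collected, categorised and reported. Nor would it generally conceal a large harm: outside the lowest assumed rate, a fivefold increase would usually be detected. What would follow is a statement that safety was demonstrated, resting on a non-significant result that cannot carry it. The change should be made, but the matter is one of specification and wording.

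**What to change.** 1. **10.4.4:** replace the present sentence with a by-arm summary of the 8.1 endpoint in all randomised patients. Give the number of events and the number of patients with at least one, with the between-arm difference or ratio and its 95% confidence interval. Because controls wear no sensor, show device-related events separately, using the relationship-to-device category that 8.1 already requires.
2. **8.1:** replace the significance criterion with this estimate and interval, and state that a non-significant difference is not to be read as evidence of safety.
3. **Section 3:** change the aim from demonstrating safety to describing or estimating it, unless a justified margin is pre-specified and the interval is compared with it.
4. **8.2.3:** keep the exclusion of mild sunburns from the endpoint, since over-reporting is expected in one arm.

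The cost is wording in three sections and one extra results table, with no added visits or patients. The case report forms are not in the documents, so it should be confirmed that they capture the relationship category. The downside is a more modest safety claim. The change should be made before the data tables are frozen and the blind is broken (10.6.3), so that the safety analysis is not chosen after the results are known.

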#### 10.4.5 ADHERENCE AND RETENTION ANALYSES

See specific Aim #8.

